13.5 Times of Statistical Analyses29

14.0 Final Report and Publications29

15.0 References30

5.0 Introduction

Treatment of rheumatoid arthritis (RA) has advanced significantly after the introduction of biological agents and improved treatment recommendations. Current treatment guidelines for the management of RA advocate the use of an TNF-inhibitor in combination with MTX as first line biological therapy. Multiple studies have shown the synergistic effect of TNF-inhibitors and MTX. In February 2011, dosage regimens of methotrexate (MTX) were approved up to until ≤ 16 mg/week in Japan (2011 Japanese Guideline for MTX treatment with RA patient). Thus physicians may prescribe MTX in a maximum dose of ≤ 16 mg/week. Moreover MTX was also approved as first-line therapy in adult patients with RA.

MTX is a low-molecular-weight disease-modifying antirheumatic drug (DMARD) that has been demonstrated highly beneficial in inducing clinical remission, preventing the progression of bone destruction, improving quality of life (QOL), and ensuring durability and safety of treatment.¹⁻⁶⁾ On the basis of its usefulness in combination with other low-molecular-weight DMARDs and biologics, MTX is positioned as an anchor drug in the treatment of RA, and is one of the most commonly used low-molecular-weight DMARD in RA.⁷⁾ The benefits of MTX in combination with biological agents have been assessed in retrospective analyses of the data of post-marketing surveillance of biologics conducted prior to the approval of high-dose MTX treatment at ≥ 10 , ≤ 16 mg/week. Safety evaluation based on the incidence and patterns of adverse drug reactions (ADRs) by dose of MTX have revealed that the ADR profile does not differ significantly between lower and higher doses of MTX. Moreover, the efficacy of treatment appears better in patients receiving MTX at higher doses, which indicates a tendency toward dose-effect relationship. These results of retrospective analyses support the necessity of prospective studies to investigate the usefulness of treatment combining biological agents and high-dose MTX.

In the present prospective post-marketing observational study (PMOS), we will investigate the effectiveness and safety of treatment with adalimumab (Humira[®]) and high-dose MTX (≥ 12 mg/week).

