7.6 Study Conduct

7.6.1 Schedule of Observations

This PMOS will be a single-arm, multi-center, prospective cohort study.

Non-interventional studies are one of several methodical instruments to collect information on drugs available on the market. Their defining characteristic is the lack of influence on the relationship between individual physicians and patients in respect to determining indication as well as choice and conduct of the treatment, while at the same time allowing for the structured and systematic collection of treatment data (see also Section 6 “Rationale”). Adalimumab must not be prescribed for the purpose of including a patient in this PMOS.

Patients will be informed about the type of therapy, alternate therapies, and risks, and they have to provide informed consent before the start of adalimumab therapy. Before enrollment in the PMOS, the patients will be made anonymous. AbbVie GK will only receive access to anonymous data. AbbVie GK can only identify the patients via their patient number.

The documentation consists of patient self-assessments as well as assessments by the physician. The following table provides an overview of the study visits with corresponding study activities (Table 1 “Study Schedule”).

Table 1. Study Schedule

Activity	Visit (Week)					
	0	12	24	52	76	104*
Patient Background	✓					
Inclusion / Exclusion criteria	✓					
Previous RA therapies	✓					
Concomitant diseases and therapies	✓	✓	✓	✓	✓	✓
Current adalimumab therapy	✓	✓	✓	✓	✓	✓
Current RA therapies	✓	✓	✓	✓	✓	✓
Effectiveness						
• DAS28	✓	✓	✓	✓	✓	✓
• CDAI	✓	✓	✓	✓	✓	✓
• SDAI	✓	✓	✓	✓	✓	✓
• HAQ	✓	✓	✓	✓	✓	✓
• EQ-5D	✓	✓	✓	✓	✓	✓
• mTSS (X-rays of Hands and Feet)	✓			✓		✓
Adverse Events		✓	✓	✓	✓	✓

* Week 104 or last visit

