“5.2.3 Summary of serious adverse drug reactions by each MTX Dose of Baseline”

Analysis object: Patients included in the safety analysis set

Purpose of analysis: To indicate the number of patients analyzed, number of patients who developed ADRs, number and percentage of ADRs, number and percentage of SOC and PT by category of MTX dose at the start of treatment regarding serious ADRs.

Note: Category of MTX dose at the start of treatment

“Baseline MTX 12<= $<$ 14.0,” “Baseline MTX 14.0<= $<$ 16.0,” “Baseline MTX 16.0<=”

This should be prepared only at the time of literature analysis.

“Table 5.2.4 Summary of serious adverse drug reactions by each MTX Dose of Baseline (Event/100 Patient Years)”

Analysis object: Patients included in the safety analysis set

Purpose of analysis: To indicate the number of patients analyzed, number of patients who developed ADRs, number and percentage of ADRs (unit: 100 persons/year), number and percentage of SOC and PT by category of MTX dose at the start of treatment regarding serious ADRs during Humira treatment.

Note: Category of MTX dose at the start of treatment

“Baseline MTX 12<= $<$ 14.0,” “Baseline MTX 14.0<= $<$ 16.0,” “Baseline MTX 16.0<=”

Percentage of patients who develop ADRs (person/year) = “number of serious ADRs / total follow-up period)

This should be prepared only at the time of literature analysis.

“Table 5.3.1 List of AEs occurred during treatment and after completion of treatment”

Analysis object: Patients included in the safety analysis set

Purpose of analysis: To indicate the number of overall ADRs, SOC and PT occurred by case status (overall, patients who are continuing Humira treatment, patients who discontinued Humira treatment) regarding AEs.

The patients who discontinued Humira treatment should be indicated by timing of treatment (during treatment, after treatment).

Note: The definitions of case status should be as follows.

- During treatment

Events that occurred between the date of initial Humira treatment and the date of final Humira treatment.

- After treatment

Events that occurred after the date of final Humira treatment.

“Table 5.3.2 List of serious AEs occurred during treatment and after completion of treatment”

Analysis object: Patients included in the safety analysis set

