Purpose of analysis: To indicate the number of overall AEs, SOC and PT occurred by case status (overall, patients who are continuing Humira treatment, patients who discontinued Humira treatment) per timing of treatment (during treatment, after completion of treatment) regarding serious AEs.

Note: The definitions of the patients who are continuing Humira treatment and the patients who discontinued Humira treatment should be same as “Table 5.3.1 List of AEs occurred during treatment and after completion of treatment.”

“Table 5.4 Incidence of ADRs by patient background factor”

Analysis object: Patients included in the safety analysis set

Purpose of analysis: To indicate the overall ADRs, and the number and percentage the patients who developed ADRs by seriousness by patient background factor. The categories of patient background factors should follow “11. Data-layer separation,” and when ADRs of the same PT occurred in the same patient, and the number of the ADR should be rounded to a severe event before tabulation.

<Detailed note>

- 1) The data at the start of Humira treatment should be analyzed.

- 2) The data during the Humira treatment should be analyzed.

“Table 5.4.1 Incidence of ADRs by patient background factor (Hospital for the University of Occupational and Environmental Health, Japan)”

Analysis object: patients included in the safety analysis set

Note: Patients treated at the Hospital of the University of Occupational and Environmental Health, Japan should be tabulated.

“Table 5.4.2 Incidence of ADRs by patient background factor (other than Hospital for the University of Occupational and Environmental Health, Japan)”

Analysis object: patients included in the safety analysis set

Note: Patients excluded from those treated at the Hospital of the University of Occupational and Environmental Health, Japan should be tabulated.

“Table 5.5.1.1 Frequency of ADRs by seriousness with or without liver disorder”

Analysis object: Patients included in the safety analysis set

Purpose of analysis: To indicate the number of patients analyzed, number of patients who developed ADRs, number and percentage of ADRs, number and percentage of SOC and PT by seriousness with or without liver disorder regarding ADRs. Additionally, the stratified items with a significant difference in Table 5.4 should also be tabulated.

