Purpose of analysis: To indicate the number of patients by evaluation time and the summary statistics of the score and the response for the joint space narrowing score and conduct a paired t test for the response from baseline. Additionally, the number and percentage of the patients by evaluation time by the category of the joint space narrowing score should be shown. The category of the joint space narrowing score should follow “11. Data-layer separation.”

Note: None in particular.

“Table 6.11.2 Percentage of patients without a trend or worsening of the joint space narrowing score (evaluation time at week 104)”

Analysis object: Patients included in the efficacy analysis set (mTSS at week 104)

Purpose of analysis: To tabulate the patients included in the efficacy analysis set (mTSS at week 104) by using the same tabulation technique as Table 6.11.1.

Note: None in particular.

“Table 7.1 Summary of MTX at each Period”

Analysis object: patients included in the safety analysis set

Purpose of analysis: to calculate the summary statistics of the MTX dose at treatment start, the mean MTX dose between treatment start and week 52, the mean MTX dose between treatment start and week 12, and the mean MTX dose between week 12 and week 52.

Note: This form should be prepared only at the time of literature analysis.

“Table 7.1.1 Summary of MTX Over Time”

Analysis object: Patients included in the safety analysis set

Purpose of analysis: To illustrate the followings by timing by a cumulative bar chart: MTX dose at treatment start, MTX dose at week 12, MTX dose at week 24, MTX dose at week 52, MTX dose at week 76, and MTX dose at week 104. At treatment start, at weeks 12, 24, 52, 76 and 104 should be established by the categories indicated in “12. Handling of data on test/evaluation time.”

Note: This form should be prepared only at the time of literature analysis.

“Table 7.1.2 Demographic data and baseline score each MTX Dose of Baseline”

Analysis object: Patients included in the efficacy analysis set

Purpose of analysis: To calculate the number and percentage of patients by patient background factor at the start of treatment, or the stratified summary statistics of MTX dose at the start of Humira treatment.

The patient background factors should follow “11. Data-layer separation.”

Note:

[Complication: liver disorders (hepatitis)]: The denominator of the percentage should be the number of patients with “hepatitis.”

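### ADR comparisons across baseline MTX dose bands are not adjusted for patient factors, so a modest dose-toxicity gradient could be attenuated or masked, and events attributed to MTX alone are not counted

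*SAP*

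**What the plan says.** SAP 10.1 and 11 sort MTX dose at the first Humira injection into three bands: 12 to <14, 14 to <16, and ≥16 mg/week. SAP 13.2 then uses these bands for safety in three tables, all in the safety analysis set.

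- **Table 5.2.3** (serious ADRs): "number and percentage of SOC and PT by category of MTX dose at the start of treatment regarding serious ADRs".
- **Table 5.2.4** (serious ADRs by exposure): "number and percentage of ADRs (unit: 100 persons/year", with the rate defined as "number of serious ADRs / total follow-up period". Of Table 5.2.3, as of this table, the SAP says "This should be prepared only at the time of literature analysis".
- **Table 5.4** (all ADRs, one background factor at a time, MTX dose being one factor in SAP 11): "To indicate the overall ADRs, and the number and percentage the patients who developed ADRs by seriousness by patient background factor". A test is implied. SAP 5(2) names chi-square, and the entry for Table 5.5.1.1 calls for further tabulation of factors that differ significantly in Table 5.4.

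SAP 13.3, Tables 7.1.2 and 7.1.3, describe background factors by MTX band ("the stratified summary statistics of MTX dose at the start of Humira treatment"), but in the efficacy set and for the literature analysis only.

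Protocol 7.6.1 describes non-interventional studies as leaving the physician free in "determining indication as well as choice and conduct of the treatment". SAP 2 and 10.2 define an ADR as an AE whose link with Humira is not ruled out.

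**The concern.** Dose is not allocated, so it can follow age, body weight, renal or liver disorder and steroid use, and these may also affect the risk of an event. A crude comparison of dose bands then mixes the effect of dose with the effect of who received it. If higher-risk patients sit in the lower bands, the two effects oppose each other and the table looks flatter than the truth.

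This bears on how the results will be read. SAP 5(1) lists factors influencing safety as an analysis item, and Tables 5.2.3 and 5.2.4 exist only to set serious ADRs against MTX dose. A crude MTX row that is not significant in Table 5.4 also triggers no further table.

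The outcome adds a second gap. An event that the physician attributes to MTX and not to Humira is not an ADR, so it drops out of the tables meant to show how reactions vary with MTX dose.

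**Working it through.** **1. Is there an adjusted safety analysis anywhere?**

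| SAP output | Outcome | By MTX band? | Adjusted for |
|---|---|---|---|
| 5.2.3 | Serious ADRs, % | Yes | Nothing |
| 5.2.4 | Serious ADRs per 100 patient-years | Yes | Length of follow-up only |
| 5.4 | All ADRs, by seriousness | Yes, one row | Nothing |
| 5.5.1.x, 5.5.2.x | ADRs by liver, renal, elderly, mode of administration | Not crossed with MTX | Nothing |
| 5.1.1, 5.3.1 | All AEs | No | Nothing |
| 6.2.6, 6.9.5.x | DAS28-4CRP remission, mTSS change | Yes, univariate | Nothing |
| 6.9.6.x | mTSS change | No | Gender, complication, stage, disease duration |

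Every regression has an efficacy outcome. The logistic entries ask for a count of patients with ADRs among the printed columns, but the modelled variable is remission or mTSS change. The protocol synopsis likewise confines regression to effectiveness.

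**2. Which events are counted?** Protocol 9.2 has the physician judge causality of adalimumab, treats the effect of another drug as a ground for calling an event unrelated, and asks for any other suspected drug to be recorded. SAP 10.2 counts anything other than unrelated as an ADR. An event suspected of both drugs is therefore in, and one attributed to MTX alone is out. The latter appears in the AE tables, which are not split by MTX dose.

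**3. How large could the distortion be?** The documents give no ADR rate, band size or risk profile by band, so there is no plan figure to reproduce. The inputs below are assumptions, apart from N = 350.

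Stronger channelling:
- 25% aged ≥65 and 30% of low weight, independent of each other.
- MTX ≥14 mg/week in 55% of younger and 25% of older patients, 15 points lower if low weight.
- ADR odds ratios 2.0 (age) and 1.5 (low weight), reference risk 30%, true MTX odds ratio 1.8.

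In each cell, odds = (0.30/0.70) × the applicable odds ratios, and risk = odds/(1 + odds).

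| Stratum | n at <14 mg | Risk | n at ≥14 mg | Risk |
|---|---|---|---|---|
| Younger, not low weight | 82.7 | 30.0% | 101.1 | 43.6% |
| Younger, low weight | 47.2 | 39.1% | 31.5 | 53.6% |
| Older, not low weight | 45.9 | 46.2% | 15.3 | 60.7% |
| Older, low weight | 23.6 | 56.3% | 2.6 | 69.8% |
| All | 199.5 | 39.0% | 150.5 | 47.9% |

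Crude odds ratio = (0.479/0.521)/(0.390/0.610) = 1.44. With a true odds ratio of 1.0, the same weights give 34.0% v 39.0%, a crude odds ratio of 0.81.

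Milder channelling (≥14 mg/week in 50% v 35%, 5 points lower if low weight; odds ratios 1.5 and 1.3) gives 47.2% v 34.6%, crude 1.69, and 0.94 under the null.

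Simulation with the same inputs (1,500 studies per scenario; 1,000 for the last row):

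| Scenario | Crude OR, rejection rate | Adjusted OR, rejection rate |
|---|---|---|
| Stronger, true 1.8 | 1.43, 37% | 1.80, 71% |
| Milder, true 1.8 | 1.70, 68% | 1.82, 76% |
| Stronger, true 1.0 | 0.80, 16% | 0.99, 5.6% |
| Milder, true 1.0 | 0.94, 5% | not shown |

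A small part of the drop from 1.8 is the non-collapsibility of the odds ratio. Risk ratios do not have that problem.

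**4. Check on the risk-ratio scale with three bands.** Let the true risk ratio per band be g, the high-risk share be q1 in the bottom band and q3 in the top band, and the risk ratio for high-risk patients be f. Then the crude top-to-bottom ratio = g² × (1 − q3 + q3·f)/(1 − q1 + q1·f). For g = 1.25, f = 2, q1 = 0.40, q3 = 0.10: 1.5625 × 1.10/1.40 = 1.23, against a true 1.56. Taking q1 from 0.40 to 0.60 with q3 = 0.10:

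| True ratio | f = 2 | f = 3 |
|---|---|---|
| 1.56 | 1.07 to 1.23 | 0.85 to 1.04 |
| 2.25 | 1.55 to 1.77 | 1.23 to 1.50 |

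If q is equal across bands, crude equals true.

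**5. Serious ADRs.** At an assumed 3 to 5% reference risk, the stronger scenario gives about 19 to 31 events. Power for a true odds ratio of 1.8 is 12 to 14% crude and 22 to 28% adjusted. Under the null, crude false positives are 4 to 8%.

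**The case against.** The case for leaving the plan alone is that no dose-toxicity hypothesis is stated. Protocol 7.0 asks for the incidence and pattern of adverse events in a single-arm study, and Tables 5.2.3 and 5.2.4 are summaries for the literature analysis with no test. Channelling is nowhere documented. Entry requires MTX ≥12 mg/week for at least three months, so patients held below that dose are already excluded, which may weaken it. Confounding could also run the other way, for example if more active disease led to higher doses. For serious events, scarcity limits the analysis more than confounding does.

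Most of this stands and sets the size of the point. It does not remove it: Table 5.4 carries an implied test on the MTX row, and a comparison biased in an unknown direction is still uninterpretable without adjustment.

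Three stronger readings are tempting, and the documents do not support them.
- A reader might infer that the plan offers only raw counts and percentages. Table 5.2.4 gives person-time rates, although these correct for follow-up, not patient risk.
- A reader might infer that any gradient is hidden. A true ratio of 2.25 stays above 1.2 throughout the grid.
- A reader might infer that the study rests on, and would simply repeat, the finding that "the ADR profile does not differ significantly between lower and higher doses of MTX". That sentence is Introduction background, from data before doses of 10 to 16 mg/week were approved. This study compares bands from 12 mg/week up, a different contrast, and Protocol 6.0 rests on effectiveness.

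**Conclusion.** The point holds in limited form. No comparison of ADRs by baseline MTX band is adjusted for patient factors, the dose is the physician's choice, and events attributed to MTX alone are not counted. Those statements come directly from the documents.

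The size is conditional. If higher-risk patients tend to receive lower doses, a true odds ratio of 1.8 appears as about 1.4 to 1.7 under the assumed inputs. A gradient near 1.56 from bottom to top band could disappear or reverse only when the risk factor is strong. With no channelling there is no distortion. The documents cannot say which case applies, and the planned background tables by MTX band use the efficacy set, not the set in which ADRs are counted. A flat crude result should therefore not be read as absence of a dose effect. The primary endpoint is unaffected.

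**What to change.** - Beside Table 5.4, add a logistic regression of any AE (yes/no) on baseline MTX dose, and the same for any ADR, each adjusted for age, body weight, renal disorder, liver disorder and corticosteroid use at start. Print crude and adjusted odds ratios with 95% CIs side by side. The any-AE model brings back events attributed to MTX alone.
- Tabulate these baseline factors by MTX band in the safety analysis set, so that channelling can be seen.
- Label Tables 5.2.3 and 5.2.4 as descriptive, and state that no dose conclusion is drawn from them. Events there are likely too few for a useful adjusted model.

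The cost is two models and one table on data already collected. Patients with a missing covariate drop out of the models, because SAP 9.1 does not impute, so the number analysed should be printed. Intervals may be wide, and confounding by unrecorded factors remains.

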10.2. Safety analysis

Name of data	Derivation and calculation methods
Adverse event	For adverse event-related data, “an AE matching list”, the data set through the matching activities (matching of CRF data and safety information data), should be used. AEs with the same patient number should be aggravated and counted as one event when the PT is the same. However, when the novelty (known/unknown) is different within the same PT, such as in Appended Form 2, they should be tabulated separately.
Seriousness of AE	For seriousness of an AE aggravated from a single patient as the same PT, seriousness set through AE matching activities should be set in the following order of priority. Serious Non-serious
Causal relationship of AE	Where the causal relationship set through AE matching is other than “not related”, the causal relationship is defined as related. For causal relationship of an AE aggravated from a single patient as the same PT, causal relationship set through AE matching activities should be set in the following order of priority. Related Not related
Outcome of AE	Outcomes of AEs aggravated from a single patient as the same PT should be set in the following order of priority. Fatal Unknown Not recovered/Not resolved Recovered/Resolved with sequelae Recovering/Resolving Recovered/Resolved
Adverse reaction	AEs of which causal relationship is other than “not related” set through the AE matching activities are defined as ADRs.
Serious AEs	AEs of which seriousness set through the AE matching activities is “serious” are defined as serious AEs.
AEs outside the follow-up period	These should be handled as outside the safety analysis. AEs are defined that occurred prior to the start date of Humira treatment or at week 108 (treatment start date + 755).

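### SAP Table 5.2.4 is headed as events per 100 patient-years, but its formula carries a patient-percentage label without the factor 100, and the same-PT rule in SAP 10.2 means recurrent serious ADRs are not counted

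*SAP*

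**What the plan says.** The entry for Table 5.2.4 in SAP 13.2 describes one quantity in four places:

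- Heading: "Summary of serious adverse drug reactions by each MTX Dose of Baseline (Event/100 Patient Years".
- Purpose: "number and percentage of ADRs (unit: 100 persons/year", limited to what is wanted "regarding serious ADRs during Humira treatment".
- Note, left side of the formula: "Percentage of patients who develop ADRs (person/year".
- Note, right side of the formula: "number of serious ADRs / total follow-up period", with no multiplier.

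The Purpose line also asks for the number of patients who had ADRs, and for SOC and PT rows within each baseline MTX category. The entry ends by limiting the table to the literature analysis.

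The counting rule is in SAP 10.2: "AEs with the same patient number should be aggravated and counted as one event when the PT is the same". Its one exception is "However, when the novelty (known/unknown) is different within the same PT, such as in Appended Form 2, they should be tabulated separately". That exception separates known from unknown events and does not bring back repeat episodes. Table 5.2.4 does not exempt itself from the rule.

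No section defines the total follow-up period used in the formula. The nearest defined term is the AE follow-up period in SAP 10.1, which runs from the first Humira dose to 755 days later.

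**The concern.** The heading promises an event rate, the formula label promises a proportion of patients, and the SAP 10.2 rule delivers a third quantity, the number of different PTs per patient summed over patients. The scale is also inconsistent: the heading and Purpose are per 100 patient-years, while the formula as printed is per one.

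Among the tables listed in SAP 13, this is the only one that puts ADRs by baseline MTX dose on a person-time scale; Table 5.2.3 gives counts and percentages only. Because it is meant for publication, readers will take the heading at face value and set the figures beside event rates per 100 patient-years from other studies. Once a patient has had a serious ADR of a given PT, later time stays in the denominator, but a recurrence in that time cannot enter the numerator.

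**Working it through.** **No figure to reproduce.** The documents give no rate, event count or person-time for this table. The check therefore works on the definitions, followed by illustrations in which every count is assumed.

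**Step 1: what the numerator becomes.** Let E be all serious ADR episodes, C the distinct patient-PT pairs left after the SAP 10.2 rule, and P the patients with at least one episode. Then P ≤ C ≤ E. C equals E only if no patient repeats a PT, and C equals P only if no patient has two different PTs. The overall rate in the Note uses C, and an SOC row does the same within its SOC. In a single PT row, C is the number of patients with that PT.

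**Step 2: small example (assumed data).** Four patients have these serious ADRs: pneumonia three times; pneumonia and zoster; zoster twice and interstitial pneumonia; interstitial pneumonia once.

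- E = 3 + 2 + 3 + 1 = 9
- C = 1 + 2 + 2 + 1 = 6
- P = 4

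| Assumed person-time | Formula as printed (C/T) | 100 × C/T | Event rate (100 × E/T) | Patients per 100 PY (100 × P/T) |
|---|---|---|---|---|
| 100 PY | 0.06 | 6.0 | 9.0 | 4.0 |
| 200 PY | 0.03 | 3.0 | 4.5 | 2.0 |

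The pneumonia row shows 2 after the rule, which is the number of patients with pneumonia, against 4 episodes.

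**Step 3: plausible size (simulation, all inputs assumed).** There are 150 patients, with a true rate of 10 serious events per 100 PY. Patient rates are gamma distributed with shape k = 5, 1 or 0.3 (weak to strong clustering), PT frequencies are Dirichlet(0.5), and each scenario has 2,000 data sets. The shortfall is 1 − C/E.

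| Follow-up and number of PTs | Shortfall, weak to strong clustering |
|---|---|
| 2 years for everyone, 8 PTs | about 4% to 11% |
| Exponential dropout, 50% at one year, 8 PTs | about 3% to 9% |
| The same dropout, 30 PTs | about 1% to 3% |

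In the first row the collapsed rates are about 9.6, 9.4 and 8.9 per 100 PY. The dropout scenarios echo the 50% loss by week 52 that protocol 13.1 assumes. For scale, 150 patients × 2 years × 0.10 = 30 events, and the Poisson relative standard error is 1/√30 ≈ 18%.

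**Step 4: the denominator.** The numerator is on-treatment, but the person-time is undefined. Assume 350 patients, all followed for the full AE period of 756 days (both end days counted): 350 × 756/365.25 = 724.4 PY. If half stop Humira at day 84, on-treatment time is 350 × (0.5 × 756 + 0.5 × 84)/365.25 = 402.5 PY. If half stop at day 364, it is 350 × (0.5 × 756 + 0.5 × 364)/365.25 = 536.6 PY. Dividing on-treatment events by the full AE period would then give 402.5/724.4 = 0.56 to 536.6/724.4 = 0.74 of the on-treatment rate. This is conditional on that reading of the term, which the SAP does not state.

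**The case against.** The strongest reply is that the SAP is consistent on its own terms. SAP 10.2 defines same patient and same PT as one event, so a heading in events and a numerator of serious ADRs agree, and only the left-hand label is odd. Tables 5.1 and 5.4 also merge repeats of a PT, and the time-of-onset rule in SAP 12 uses first occurrences. Counting every episode would then be a preference. This stands in part: one count per PT per patient is a legitimate choice. It does not rescue the heading, because a reader of the published table will take "Event/100 Patient Years" in its usual sense, and nothing in the entry says that recurrences are left out. The label contradicts the heading either way.

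Other limits stand and narrow the point:

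- A reader might infer that the printed values will be 100 times too small. The documents do not support that. The Purpose line gives the per-100 unit, so a programmer can infer the multiplier; the Note contradicts the rest of the entry and should be corrected.
- A reader might infer that the figure is neither an event nor a patient measure in any row. In a PT row it is a count of patients with that PT over person-time.
- A reader might infer that a dose group with recurrent serious infections is made to look safer. Nothing in the documents shows that same-PT recurrence differs between the MTX categories.
- A larger shortfall would follow if patients alone were the numerator, but the right side of the formula counts ADRs, and the number of patients is already planned as a separate item.

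**Conclusion.** The entry contradicts itself on label and scale. Combined with SAP 10.2, its overall and SOC rates understate an event rate whenever a serious ADR of the same PT recurs in a patient. This can be read directly from the text. The size cannot: the range of about 1% to 11% rests entirely on assumed event rates, clustering, follow-up and number of PTs. In the base scenario it is smaller than the 18% sampling error of a table with 30 events. The undefined person-time could matter more, but only if off-treatment time is in fact included.

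The table is descriptive, no test is planned on it, it serves only the literature analysis, and the primary endpoint is unaffected. It should still be corrected before publication, because as written it would present a count of patient-PT pairs as an event rate.

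**What to change.** In the Note to Table 5.2.4, replace the formula and its label with: serious ADR event rate per 100 patient-years = 100 × number of serious ADR episodes during Humira treatment / total patient-years. Exempt this rate from the same-PT rule in SAP 10.2, and add a footnote that its counts therefore differ from those in Table 5.2.3. Keep the restriction to events during Humira treatment; dropping it would bring in post-treatment events.

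If the sponsor prefers the SAP 10.2 count, keep it, write in the factor 100, and change the heading and label to say that each PT is counted once per patient.

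In either case, show the already planned number of patients with a serious ADR in its own column, and state which person-time the total follow-up period means, so that it matches the on-treatment numerator.

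The cost is a few lines of SAP text and, under the first option, a recount for one table, with rates that will be slightly higher if any same-PT recurrences occurred.
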